#### **9.1.3. Missing Data**

Missing data will not be imputed by any method.

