## 5.2. Withdrawal of Subjects

While withdrawal is discouraged, subjects may withdraw from the registry at any time, with or without reason and without prejudice to further treatment. In all cases of withdrawal, the reason(s) for withdrawal (if given) will be recorded upon registry termination.

In addition, the Investigator may withdraw the subject due to any reason determined by the Investigator to be in the best interest of the subject.

Subjects withdrawn from the registry prior to hemostasis (e.g., after enrollment and prior to deployment of the collagen plug) should be converted to conventional means (manual compression) to achieve hemostasis.

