##### Ambulation

Subjects should be ambulated according to institution's standard practice. Any incidents of delay in ambulation (> 1 hour beyond stated standard of care for each site) should be documented on the Ambulation eCRF and a Protocol Deviation eCRF should be completed for non-medical delays > 1 hour. Record the following information on the Post-Procedure Source Data Worksheet provided by the Sponsor (required):

- **T7** TTA: time that subject was able to stand and ambulate at least 20 feet without evidence of arterial re-bleeding at the access site.

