## **7.6. Study Exit**

Once the subject has completed the follow-up visit or has withdrawn, they should be exited from the registry provided they do not have any conditions that require continued follow-up. The date of exit and subject status will be recorded.

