### **8.2. Secondary Procedural Outcomes - Performance**

Time to ambulation (TTA) is defined as elapsed time between device removal and when subject first stands and walks 20 feet without evidence of arterial re-bleeding from the access site. The time to ambulation will be measured in hour (hh):minutes (mm). (TTA = T7 – T5).

Time to discharge (TTD) is defined as elapsed time between device removal and when subject is actually discharged from the facility. The time to ambulation will be measured in hour (hh):minutes (mm). (TTA = T8 – T5).

Device Success is defined as the ability to deploy the delivery system, deliver the collagen, and achieve hemostasis with the Cardiva VASCADE™ VCS alone or with adjunctive compression.

Procedure Success is defined as attainment of Device Success and freedom from major access site closure-related complications through 30 days.

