## **9. Statistical Considerations**

### **9.1. Analysis Populations and Data Handling Conventions**

#### **9.1.1. Intent to Treat (ITT) Population**

All subjects who receive any portion of the Cardiva VASCADE™ VCS device treatment under this protocol (i.e., intention to enroll acknowledged by Investigator prior to introduction of the device; subject is then enrolled at time of device introduction) will be included in the primary, ITT performance and complication analyses.

Subjects who do not receive any portion of the VASCADE™ VCS but instead receive manual compression, a VASCADE VCS commercial device (i.e., outside of the registry), or another approved closure device instead (i.e., by error or by Investigator choice), will not be enrolled and are therefore excluded from all analyses.

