## **9.2. Statistical Analysis Plan**

### **9.2.1. General Analysis Principles**

As a descriptive study, mean, standard deviation, median, minimum and maximum will be reported for continuous variables. Frequencies and proportions will be reported for categorical variables. Ninety-five percent confidence intervals will be reported for outcome summaries, e.g. mean and median for time to hemostasis (TTH), time to ambulation (TTA), and time to discharge (TTD), and Wilson score confidence intervals for proportions of device success and procedure success.

Since the critical limb ischemia population encompasses a broad spectrum of disease severity and comorbidities, both performance and complication outcomes will be presented overall and by the following subgroups: Rutherford score  $\leq 5$  vs. 6 (i.e., tissue loss), index intervention above knee v. at/below knee, gender, presence vs. absence of diabetes mellitus, BMI  $\leq 30$  vs.  $> 30$ , and inpatient vs. outpatient facility procedures. Additionally, TTA and TTD will also be presented overall and by no delay vs. delays related to the access site vs. delays due to other causes, as reported by the Investigator.

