## 9.2.3. Complication Outcomes

### 9.2.3.1. Primary Complication Outcome Analysis

The primary complication outcome analysis will be based on the 30-day patient incidence rate of combined major access site closure-related complications for the ITT and PP cohorts, as described in Section 9.1. The proportion of subjects with any major access site closure-related complications will be reported with 95% Wilson core confidence intervals. For each particular major complication listed in Section 8.3, the proportion of subjects reporting it will also be summarized.

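### The TTA summary leaves out any subject who never walks, and the plan does not say how subjects without a day 23–37 contact count in the 30-day outcomes

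*Combined protocol and SAP*

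**What the plan says.** - **Analysis set.** Section 9.1.1 says that everyone who receives any portion of the device under the protocol "will be included in the primary, ITT performance and complication analyses".
- **Missing data.** Section 9.1.3 consists of one sentence: "Missing data will not be imputed by any method". It says nothing on denominators, censoring or sensitivity analysis.
- **TTA.** Section 8.2 defines TTA as "elapsed time between device removal and when subject first stands and walks 20 feet without evidence of arterial re-bleeding from the access site", computed as T7 − T5. Section 7.4.4 (Ambulation) records T7 as the "time that subject was able to stand and ambulate at least 20 feet without evidence of arterial re-bleeding at the access site".
- **Summary method.** Section 9.2.1 says "mean, standard deviation, median, minimum and maximum will be reported for continuous variables", with 95% confidence intervals for the mean and median of TTA. Section 9.2.2.3 refers back to this. No time-to-event or rank-based method is named.
- **30-day outcomes.** Section 9.2.3.1 says "The proportion of subjects with any major access site closure-related complications will be reported with 95% Wilson core confidence intervals". Procedure Success (Section 8.2) needs Device Success and no major complication up to day 30, and Section 7.5 relies on the day 23–37 telephone contact to establish it.
- **Early exit.** Section 5.2 allows withdrawal at any time, and Section 7.6 says "Once the subject has completed the follow-up visit or has withdrawn, they should be exited from the registry". No section says how a subject who leaves before the final contact enters the 30-day proportions.

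**The concern.** T7 comes into being only when the subject walks the required distance without arterial re-bleeding. A subject who never does so has no TTA value, and the reason is the outcome itself. With imputation ruled out and a mean and median of observed times prescribed, that subject cannot enter the TTA summary, although Section 9.1.1 promises that all ITT subjects are in the performance analyses. The reported figure is then a time among those who walked.

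The 30-day outcomes raise a different problem. The final contact settles the status of a subject who has had no event so far. If it is missing, Section 9.1.1 points to keeping the subject, Section 9.1.3 forbids assigning a value, and Section 9.2.3.1 gives no denominator. Two analysts could report different rates from the same data.

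No hypothesis test depends on this. At stake are the published estimates, which are the only product of a descriptive registry. Section 1.1 itself says that inconsistent methods and definitions hinder comparison across published studies of these devices.

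**Working it through.** There is no figure in the plan to reproduce. Section 9.3 sets 100 subjects by judgement, without a precision target, event rate or dropout rate.

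**Inputs**
- N = 100 (Sections 4.2 and 9.3; the actual number may be smaller).
- From the pivotal RESPECT trial, Instructions for Use, Table 4, interventional device arm: TTA n = 139, mean 5.0 h, SD 6.7 h, median 4.1 h, maximum 78.0 h.
- The number of never-ambulators (k) and of subjects with unknown 30-day status (m) are assumptions, because the documents give no rate for either.

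**1. TTA median**

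Rank the k never-ambulators last. The median of all 100 subjects is then the 50/(100 − k) quantile of the observed times. Taking those times as lognormal with median 4.1 h, the all-subject median is 4.1 × exp(σ × z), where z is the normal quantile of 50/(100 − k). Two values of σ bracket the spread:
- from the mean: σ = √(2 ln(5.0/4.1)) = 0.63;
- from the SD: σ = √(ln(1 + (6.7/5.0)²)) = 1.01.

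| k of 100 | Quantile of observed times | Median if omitted | Median if ranked last |
|---|---|---|---|
| 1 | 50/99 = 0.505 | 4.1 h | 4.13–4.15 h |
| 5 | 50/95 = 0.526 | 4.1 h | 4.27–4.38 h |
| 10 | 50/90 = 0.556 | 4.1 h | 4.48–4.72 h |

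The shift is 0.03–0.05 h, 0.17–0.28 h and 0.38–0.62 h. It always goes the same way.

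**2. TTA mean**

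A never-ambulator has no value to average. As an illustration only, assign each the RESPECT maximum of 78 h:
- k = 1: (99 × 5.0 + 78)/100 = 5.73 h;
- k = 5: (95 × 5.0 + 5 × 78)/100 = 8.65 h.

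The mean therefore depends heavily on an arbitrary assigned value.

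**3. 30-day major complication rate, no events observed**

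Wilson 95% interval with p = x/n and z = 1.96: [p + z²/2n ± z√(p(1−p)/n + z²/4n²)] / (1 + z²/n). For x = 0 the upper limit reduces to z²/(n + z²); for example, 3.84/103.84 = 3.70% at n = 100.

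| m of 100 | Dropped | Counted event-free | Counted as events |
|---|---|---|---|
| 2 | 0/98: 0–3.77% | 0/100: 0–3.70% | 2/100: 0.55–7.00% |
| 5 | 0/95: 0–3.89% | 0/100: 0–3.70% | 5/100: 2.15–11.18% |
| 10 | 0/90: 0–4.09% | 0/100: 0–3.70% | 10/100: 5.52–17.44% |

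**4. Direction at 30 days**

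With 1 observed event and 5 unknown, dropping gives 1/95 = 1.05% and keeping them as event-free gives 1/100 = 1.00%. Here dropping is the less favourable choice.

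Now assume true risks of 2% in 95 completers and 10% in 5 non-completers, so the true rate is (1.9 + 0.5)/100 = 2.40%. Let f be the share of the non-completers' events seen before exit.
- Dropping all non-completers gives 1.9/95 = 2.00%.
- Dropping only those with no known event gives (1.9 + 0.5f)/(95 + 0.5f): 2.00%, 2.26% or 2.51% for f = 0, 0.5 or 1.
- Counting unknowns as event-free gives (1.9 + 0.5f)/100, that is 1.90% to 2.40%.

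The error can be downward or upward.

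**The case against.** **Slow is not the same as missing.** A subject kept in bed usually has a late T7 rather than none. Entry requires the ability to walk 20 feet (Section 5.1.1). Long ambulation delays are documented (Section 7.4.4), TTA is shown by cause of delay (Section 9.2.1), and conversions to manual compression are reported (Section 9.2.2.1). In RESPECT all 275 device subjects in the complication table have a TTA. This is fair, and it is why the effect is probably small. It does not close the gap, because the breakdown by delay also needs a T7. RESPECT also excluded clinically significant peripheral vascular disease, which this registry treats, and the registry allows planned minor amputation.

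**Observed-case reporting is normal in a descriptive single-arm registry.** That is true, but the summary should then be labelled so, and Section 9.1.1 says otherwise.

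**Stronger readings that the documents do not support.**
- A reader might infer that the no-imputation rule drops everyone who exits before day 30, so that the complication rates and Procedure Success flatter the device. No section says these subjects are dropped, and Section 9.1.1 points to inclusion. Section 1.1 aims at consistency with RESPECT, which kept its two treated non-completers: 420 − 3 withdrawn at once = 417 = 275 + 142, of whom 415 completed. Under Section 13.3 required events are recorded from enrollment to exit, so an earlier complication still counts. A device failure is already a known Procedure Success failure. Step 4 of the working shows that the direction is not fixed.
- A reader might take the slowest RESPECT subject as the measure of the effect: without the 78 h value the mean falls from 5.0 h to (695 − 78)/138 = 4.47 h. That subject did walk, has a T7 and would stay in under Section 9.1.3. The figure shows that the mean is fragile, not what this rule would remove.

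**Conclusion.** The TTA part holds. As written, the plan yields an observed-case TTA under an ITT label, and the omission of never-ambulators can only make TTA look faster. The median shifts by about 0.03–0.05 h for 1 never-ambulator in 100 and 0.38–0.62 h for 10. This rests on an assumed count and on a lognormal shape borrowed from RESPECT. The mean could move more, but it has no defined value for these subjects.

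The 30-day part holds only as an unstated counting rule. The choice between dropping unknowns and counting them event-free hardly matters: the upper limit is 3.7–4.1% with no events. The wide gap is to the worst case, at 7.0%, 11.2% or 17.4% for 2, 5 or 10 unknown. These are outer bounds and not forecasts, since RESPECT had 2 treated non-completers in 417 and no major complication. A favourable bias in the 30-day outcomes is not shown.

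This is worth correcting before analysis because the remedy is cheap. It does not undermine the design.

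**What to change.** **TTA (Sections 9.1.3 and 9.2.2).** Report the median with its 95% confidence interval in all ITT subjects, with those who never ambulated ranked last, that is, kept as not ambulated beyond the longest observed time. Give the number who never ambulated, and label the mean and SD as observed cases only. Ranking assigns no numerical value, so it can stand beside the no-imputation rule if Section 9.1.3 says so. A Kaplan-Meier median with censoring at discharge is not a good substitute. It assumes that a subject discharged without walking is like those still to walk, whereas not walking is itself the outcome.

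**30-day outcomes (Sections 9.1.3 and 9.2, for the complication rates and Procedure Success).** State that all ITT subjects stay in the denominator. Report the number with unknown 30-day status. Add a best-case row (unknowns counted as event-free) and a worst-case row (unknowns counted as events or failures). For Procedure Success, subjects already known to have failed stay failures in both rows.

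**Cost.** A few sentences and a few table rows, using data already collected. The reported figures may become slightly less favourable.

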## **9.2. Statistical Analysis Plan**

### **9.2.1. General Analysis Principles**

As a descriptive study, mean, standard deviation, median, minimum and maximum will be reported for continuous variables. Frequencies and proportions will be reported for categorical variables. Ninety-five percent confidence intervals will be reported for outcome summaries, e.g. mean and median for time to hemostasis (TTH), time to ambulation (TTA), and time to discharge (TTD), and Wilson score confidence intervals for proportions of device success and procedure success.

Since the critical limb ischemia population encompasses a broad spectrum of disease severity and comorbidities, both performance and complication outcomes will be presented overall and by the following subgroups: Rutherford score  $\leq 5$  vs. 6 (i.e., tissue loss), index intervention above knee v. at/below knee, gender, presence vs. absence of diabetes mellitus, BMI  $\leq 30$  vs.  $> 30$ , and inpatient vs. outpatient facility procedures. Additionally, TTA and TTD will also be presented overall and by no delay vs. delays related to the access site vs. delays due to other causes, as reported by the Investigator.

## 9.2.2. Performance Outcomes

### 9.2.2.1. Primary Performance Outcome Analysis (TTH)

The primary performance outcome to be described is time to hemostasis (TTH) as defined in Section 8.1. Summary statistics for TTH (mean, standard deviation, median, minimum, and maximum) will be reported for the ITT and PP subject cohorts, and as described in Section 9.1. Ninety-five percent confidence intervals will be presented for means and medians. The proportions of enrolled Cardiva VASCADE™ VCS subjects converted to manual compression will also be reported.

### 9.2.2.3 Secondary Performance Outcomes Analyses

Secondary performance outcomes to be reported include time to ambulation (TTA), time to discharge (TTD), and proportions of device success and procedure success as defined in Section 8.2 in both the ITT and PP cohorts. The analyses will be as described in Section 9.2.1.

## 9.2.3. Complication Outcomes

### 9.2.3.1. Primary Complication Outcome Analysis

The primary complication outcome analysis will be based on the 30-day patient incidence rate of combined major access site closure-related complications for the ITT and PP cohorts, as described in Section 9.1. The proportion of subjects with any major access site closure-related complications will be reported with 95% Wilson core confidence intervals. For each particular major complication listed in Section 8.3, the proportion of subjects reporting it will also be summarized.

### 9.2.3.2. Secondary Complication Outcome Analysis

The secondary safety analysis will be based on the 30-day patient incidence rate of combined minor access site closure-related complications for the ITT and PP cohorts. The proportion of subjects with any minor access site closure-related complications will be reported with 95% Wilson core confidence intervals. For each particular minor complication listed in Section 8.4, the proportion of subjects reporting it will also be summarized.

Additionally, all reported adverse events will be summarized, and will be mapped to standard terms. The number and proportion of subjects reporting any given adverse event will be tabulated according to the worst severity reported up to the 30 day follow-up. Separate tables will be constructed for (a) all reported adverse events, (b) device related adverse events, (c) serious device-related adverse events, and (d) all serious adverse events.

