**Table 1. Registry Event Schedule**

	Up to 8 Weeks Before Procedure	Procedure	Post-Procedure/ Hospital Discharge	1-15 Days Post-Procedure	23-37 Days Post-Procedure
Informed Consent 	X				
Demographics/ Medical History / Risk Factors	X				
Index limb assessment 	X		X	X	X
Femoral access site assessment (angiographic)		X	X	X	X
Anticoagulant/antiplatelet regimen 	X	X	X		
Pre-op Inclusion / Exclusion Criteria assessment	X				
Laboratory tests 	X				
Intra-procedural Exclusion Criteria assessment & acknowledgement of intent to enroll		X			
Treated with VASCADE VCS		X			
TTH determination		X			
TTA determination			X		
TTD determination			X		
Procedure Success		X			X
Adverse Events 		X	X	X	X
Office Visit				X	
Telephone follow-up					X

 If informed consent is obtained > 30 days prior to procedure, the subject's verbal re-confirmation of consent should be documented in the medical record prior to the procedure.

 Index limb assessment includes Rutherford Classification, assessment of peripheral pulses, any wounds, amputation history and/or planned amputation, existing neuropathy, and ambulatory status.

 Specific medication regimen within 24 hours prior to enrollment through completion of index procedure.

 For subjects on warfarin, INR should be taken within 24 hours before procedure. "Laboratory tests" refer to exclusion criteria requirements, according to standard of care for these procedures at each site.

 Required adverse event reports: serious, device-related injury or death; minor or major access site closure-related complications; any event that is deemed by Investigator to be clinically significant AND related to the device, the access site or the index limb (See Section 13).

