## 13.2. Reporting Guidelines

### 13.2.1. Serious Adverse Events or Injuries

- Complete Adverse Event eCRF within 24 hours of knowledge of any Serious Adverse Event.
  - Events will be categorized for seriousness by both Good Clinical Practice Guidelines (GCP), and by 21 CFR 803 MDR Reporting requirements.
- Complete device-related questions on AE eCRF. IF AE is marked as "Related to VCS", an email notification will then be sent to Cardiva Medical Complaint Handling and to the CRO for follow-up. You may be prompted to complete a Device Performance/Complaint eCRF.
- Follow institution's IRB adverse event reporting requirements, as applicable.

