## 13.3. Registry Reporting Requirements for Adverse Events

The following adverse events must be reported in this post-market registry:

- serious, device-related adverse events (i.e., "reportable")
- major or minor access site closure-related complications (serious and non-serious), as defined in Section 8
- any adverse event that, in the Investigator's opinion, is clinically significant AND is any one of the following:
  - device-related
  - access site-related
  - access limb-related.

1. Complete an Adverse Event eCRF within 24 hours of knowledge of a reportable event. Medical records (e.g., procedure notes, operative notes, discharge summary, relevant progress notes, imaging or lab studies) may be requested by Cardiva Medical or its designee for event review and potential adjudication.

2. For questions, contact [name] at [contact].

All required adverse events (AE) (serious and non-serious) will be recorded on the eCRF and monitored from the time of enrollment through study exit.

In addition to 21 CFR 803 seriousness definitions, the following definitions for Serious Adverse Events will be used for consistency with published comparative data (per GCP, E6).

A serious adverse event (SAE) is defined as an event which leads to:

- Death due to any cause
- Life-threatening condition
- Results in persistent or significant disability/incapacity
- Requires in-patient hospitalization or prolonged hospitalization
- Necessitates an intervention to prevent a permanent impairment of a body function or permanent damage to a body structure
- Results in congenital abnormality

The following definitions for rating severity of adverse events will be used:

- Mild: Awareness of signs or symptoms, but easily tolerated; are of minor irritant type; causing no loss of time from normal activities; symptoms would not require medication or a medical evaluation; signs or symptoms are transient.
- Moderate: Interferes with the subject's usual activity and/or requires symptomatic treatment.
- Severe: Symptom(s) causing severe discomfort and significant impact of the subject's usual activity and requires treatment.

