### SERIOUS ADVERSE EVENT (SAE)

A "serious injury" which must be reported to FDA is a device-related death or a device-related injury as defined in 21 CFR 803, which:

- Results in death;
- Is life-threatening – substantial risk of dying at the time of the AE, or use or continued use of the device might have resulted in the death of a patient;
- Results in permanent impairment or damage to a body structure or function, excluding trivial impairment or damage

- Necessitates medical or surgical intervention to preclude permanent impairment of a body function or permanent damage to a body structure

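### The planned table of all serious adverse events is not assured to be complete, because the protocol's collection rules and SAE definitions conflict

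*Combined protocol and SAP*

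**What the plan says.** **The analysis.** Section 9.2.3.2 plans four adverse-event tables: all reported events, device-related events, and then "c) serious device-related adverse events, and (d) all serious adverse events".

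**The narrow collection rule.** Section 13.3 opens its list with "The following adverse events must be reported in this post-market registry" and gives three categories: serious events that are device-related; the major and minor closure-related complications of Section 8; and "any adverse event that, in the Investigator's opinion, is clinically significant AND is any one of the following", namely related to the device, the access site or the access limb. It then says "All required adverse events (AE) (serious and non-serious) will be recorded on the eCRF and monitored from the time of enrollment through study exit", so the form follows the required list. Table 1 footnote 5 repeats the rule, beginning "Required adverse event reports: serious, device-related injury or death". Section 15.5 also asks investigators to report serious, device-related injuries and deaths.

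**The broad collection rule.** Section 13.2.1 says "Complete Adverse Event eCRF within 24 hours of knowledge of any Serious Adverse Event", with no condition on relatedness.

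**Two meanings of SAE.** Section 13.3 adopts the GCP list, in which death counts whatever its cause and hospitalization counts as serious. The Section 18.2 entry headed Serious Adverse Event describes an injury that "must be reported to FDA is a device-related death or a device-related injury as defined in 21 CFR 803"; it does not list hospitalization. Section 13.2.1 says seriousness will be categorized under both GCP and 21 CFR 803. Section 9.2.3.2 does not say which of the two feeds tables (c) and (d).

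**The concern.** Table (d) adds to table (c) only through serious events that are not device-related. Under the narrow rule, some of these are never required on a form: a death or hospital admission that the investigator considers unrelated to the device, access site and limb. A reader of the final report would take a table with this title as the complete count of serious events over 30 days, and would read its rate as lower than it was.

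The narrow rule also makes collection depend on the investigator's own judgement of relatedness and clinical significance. An event wrongly called unrelated may not be recorded, so that judgement could not be checked later.

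Section 13.3 says the GCP definitions are used so that results can be set beside published data, and Section 1.1 justifies the registry by inconsistent definitions and reporting in earlier studies. A serious-event table of uncertain scope works against both aims.

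**Working it through.** The plan states no figure on this point. Section 9.3 says that the sample size of 100 was not derived, and no SAE rate is given. The check is therefore a comparison of the rules, followed by an illustration on assumed rates.

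**Step 1: what each reading puts in table (d).**

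| Rule followed | Serious events collected | Effect on table (d) |
|---|---|---|
| 13.3 list and footnote 5 | Device-related; listed complications; clinically significant access-site or limb events | Wider than (c), but without unrelated deaths and hospitalizations |
| 13.2.1 with the GCP definition of 13.3 | Any SAE, any cause | Complete |
| 13.2.1 with the 18.2 definition | Device-related only | 13.2.1 adds nothing; if 18.2 also decides seriousness, (d) equals (c) |

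The first set is contained in the second, so departure from the broad rule can only lower the count. The choice of definition also touches table (c): a device-related hospitalization is serious under GCP, but Section 18.2 does not list hospitalization as a criterion.

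**Step 2: deaths.** The synopsis sends deaths to the independent adjudicator as a category of their own. The adjudicator entry in Section 18.2 lists only events that are both serious and device-related, plus major and minor complications. The 13.3 list has no item for unrelated deaths.

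**Step 3: outcomes that are safe.** Major and minor closure-related complications are required by Section 13.3 and by footnote 5. The outcomes of Sections 8.3 and 8.4 therefore do not depend on which rule is used.

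**Step 4: illustration (assumed rates, N = 100).** Let p be the true 30-day risk of any SAE, s the share of those subjects inside the 13.3 scope, and f the share of subjects at sites using the broad rule.

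Expected subjects in table (d) = 100 × p × [f + (1 − f) × s].

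With s = 50%:

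| p | Narrow rule everywhere (f = 0) | Even mix (f = 0.5) | Broad rule everywhere (f = 1) |
|---|---|---|---|
| 5% | 2.5 | 3.75 | 5 |
| 10% | 5 | 7.5 | 10 |
| 20% | 10 | 15 | 20 |

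With s from 25% to 75%, the narrow rule gives 1.25 to 3.75 of 5, 2.5 to 7.5 of 10, and 5 to 15 of 20.

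The chance that at least one of 100 subjects has an out-of-scope SAE is 1 − [1 − p(1 − s)]^100. Over the same range of s:

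- p = 5%: from 1 − 0.9875^100 = 72% to 1 − 0.9625^100 = 98%.
- p = 10%: from 1 − 0.975^100 = 92% to 1 − 0.925^100 = 99.96%.
- p = 20%: at least 1 − 0.95^100 = 99.4%.

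These figures show how the count moves with the rule. They do not estimate the shortfall in this registry.

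**The case against.** Several points on the other side have force.

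- **Reported events only.** The four tables follow a sentence saying that all reported adverse events will be summarized, so (d) can be read as the serious subset of what was reported. This has some support. But table (a) carries the word reported and (d) does not, and Section 13.2.1 still asks for more than Section 13.3. The reading makes the table fillable without making its title accurate.
- **Two seriousness systems by design.** Sections 13.2.1 and 13.3 say so: 21 CFR 803 for device reporting, GCP for comparison with published data. This stands. What remains is a glossary entry that gives the 803 concept under the SAE heading, and an analysis section that does not choose between the two.
- **Tables (c) and (d) still differ.** A serious access-site or limb event that is not device-related is collected under Section 13.3. This stands; the tables coincide only if Section 18.2 displaces Section 13.3.
- **Deaths would be seen.** A Study Exit form is completed for every enrolled subject (Section 10), subject status is recorded (Section 7.6), and the synopsis has deaths adjudicated. In footnote 5, death might even be parsed as free of the device-related condition. A death should thus be visible somewhere, but the footnote refers to Section 13, whose list has no such item, and none of this clearly puts an unrelated death on an adverse-event form.

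A reader might infer that table (d) cannot be filled, that it will understate events, or that sites will differ. The documents do not support that much. If every site applied Section 13.2.1 with the GCP definition, (d) would be complete. Site differences are an inference, and standardized forms, automatic data review, monitoring and central instruction could reduce them, though these have no single rule to enforce.

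**Conclusion.** The point holds as a conflict of scope. Completeness of table (d) is not assured. If sites follow Section 13.3 and footnote 5, the table will omit unrelated deaths and hospitalizations and will understate serious events relative to its title. The direction follows from the rules, because one collected set contains the other. The size is unknown; the counts above rest wholly on assumed values of p and s.

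The consequence is confined to the descriptive adverse-event tables. No SAE rate is a primary or secondary outcome and none is tested. It would be wrong to infer that the major or minor complication rates, or Procedure Success, are affected. The correction is still worth making, because it costs almost nothing and the table's title would otherwise promise more than the required reports support.

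**What to change.** Use one collection rule in Sections 13.2.1, 13.3 and 15.5, Table 1 footnote 5 and Section 18.2. Either option will do:

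1. Record every SAE under the Section 13.3 GCP definition, whatever its relation, from enrollment to study exit. The cost is a few extra adverse-event forms. On the assumed ranges, the extra subjects number 100 × p × (1 − s), from 1.25 (p = 5%, s = 75%) to 15 (p = 20%, s = 25%).
2. Keep the limited scope, retitle table (d) *serious adverse events among those required to be reported under 13.3*, align Section 13.2.1, and state that unrelated SAEs were not systematically collected. This has no data cost.

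In both cases:

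- State in Section 9.2.3.2 that the Section 13.3 GCP definition decides seriousness in tables (c) and (d).
- Relabel the Section 18.2 entry as the 21 CFR 803 serious-injury term and refer readers to Section 13.3 for SAE.
- Reconcile the synopsis and the Section 18.2 adjudicator entry on whether all deaths go to the adjudicator.

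These last three are wording changes only.
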